11.7 Protocol waivers to entry criteria

Protocol adherence is a fundamental part of the conduct of a randomised study. There will be no waivers regarding eligibility (i.e. each participant must satisfy all the eligibility criteria). Changes to the approved inclusion and exclusion may only be made by a substantial amendment to the protocol.

Before entering a patient onto the study, the PI or designee will confirm eligibility. If unsure whether the potential participant satisfies all the entry criteria and to clarify matters of clinical discretion investigators should contact the OP Non-STOP central study team, who will contact the CI or designated clinicians as necessary. If in any doubt, the CI or joint lead grant applicant must be consulted before recruiting the patient. Details of the query and outcome of the decision must be documented in the Investigator Site File (ISF)/Trial Master File (TMF).

11.8 Clinical queries and protocol clarifications

Every care has been taken in drafting this protocol. Contact can be made with the OP Non-STOP central study team for clarification if any instructions seem ambiguous, contradictory or impractical. Clinical queries may also be directed to the central study team. Minor administrative corrections or clarifications will be communicated to all study investigators for information as necessary. For urgent safety measures or changes that require protocol amendment see section 28.8 Urgent safety measures.

12 SCREENING AND RECRUITMENT

Participation will be offered regardless of the patients' or their parents' gender, sexual orientation, ethnicity, religion or belief, disability, or socio-economic status.

12.1 Participant Identification

Participants will be screened and then approached for potential recruitment from a minimum of 28 NHS hospitals in the United Kingdom.

The following methods will be used to identify potentially eligible participants:

• Identification during routine orthopaedic out-patient clinic visits and/or acute admissions

All patients with new radiographic evidence of Perthes' disease will be assessed for eligibility by a member of the research team.

12.1.1 Identification of participants during routine orthopaedic out-patient clinic visits and/or acute admissions

Potentially eligible patients and their parents identified during routine orthopaedic out-patient clinic visits and/or acute admissions at participating centres will be provided with the participant information material (i.e. a link to the study website and access to the patient information materials) by a member of their usual care team (who may also be a member of the site research team) and asked to consider the study.

Where their usual care clinician is not a member of the site research team, potential participants will be asked if it would be acceptable for their name and contact details to be passed to the site research team. If acceptable, the research team will make contact at a later time point (this may be in person in a clinic or via telephone or video call in accordance with local site practice) or during a further routine clinic visit. Potential participants may also be given the online PIS.

Potential participants and their parent are approached for permission for their details to be passed onto the site research team – if this permission is given this should be recorded in their clinical notes.

12.1.2 Identification through study advertising material

Social media might be used to advertise the study. All patient facing materials will be approved by REC/Health Research Authority (HRA) prior to use.

12.2 Re-screening if a potential participant does not meet inclusion/exclusion criteria first time round

If a potential participant does not meet the inclusion/exclusion criteria at first assessment, they can be re-screened – there is no time limit on when this can occur.

12.3 Use of screening logs

A screening log (within the REDCap study database) will be used to record information about the number of patients assessed for eligibility and reasons for exclusion or declined consent. Personal identifiable data will not be recorded on the screening log; a screening number will be assigned to each patient screened. The screening logs will contain non-identifiable information such as the child's age, sex, deprivation score and ethnicity.

Screening data will be reviewed each month by the study management team to assess whether representative samples of patients are being approached and to ensure no selection bias occurs in any of the centres with regard to the inclusion/exclusion of specific groups of patients.

Continued training of site staff on accurate and inclusive screening and recruitment will be through newsletters, regular Q&As/top tips, and refresher sessions. Investigator meetings will be planned, as they have proved successful in the past in ensuring appropriate sampling of patients.

13 STUDY INTERVENTION AND COMPARATOR

Participants will be randomised to either:

13.1 Containment surgery (intervention)

Participants randomised to containment surgery will receive an operation on their hip, which will typically be undertaken within three months of randomisation.

All participating centres are familiar with the surgical technique. The surgical technique seeks to embrace the vulnerability of the plastic epiphysis by ensuring it rests firmly within the acetabulum during femoral head collapse. This is achieved through an osteotomy, which includes either an osteotomy to the femur and/or pelvis (typically a femoral varus osteotomy, Salter osteotomy or shelf osteotomy). Soft tissue releases may also be performed alongside the osteotomy surgery. These surgical interventions are amongst the most common interventions performed in children's orthopaedic surgery and are therefore familiar to all children's orthopaedic surgeons. In this pragmatic study the surgeon should follow the technique that is familiar to them as per their usual practice.

Post-operative care will follow local practice. After surgery a period of restricted weight bearing on the affected leg is commonplace, as is a period of complete immobilisation with/without a spica cast. Physiotherapists and occupational therapists will support postoperative recovery, providing wheelchairs and walking aids, adaptations for school and home environments, all individually tailored. A careful record will be made of the operative details and rehabilitation provision. The use of physiotherapy will be at the discretion of the clinical team as per their standard practice and is typically

facilitated through community physiotherapists local to the child's home. Local physiotherapists will have access to a network of study trained physiotherapists for support and families will have access to online material to facilitate post operative rehabilitation at home.

13.2 Active Containment – The Non-STOP Therapy Package (Non-Surgical Containment of Perthes' disease) (comparator/control)

Participants randomised to the active containment arm will receive a package of rehabilitation, delivered through the Non-STOP best practice therapy session.

Children and families will receive a personalised individual face-to-face best practice therapy session of up to 90 minutes with a study-trained physiotherapist at the recruiting hospital/regional specialist centre.

Children will be assessed to identify their main problems and recovery goals. They will be provided with individually tailored advice, including: a review of walking aids, reassurance, education about the condition and natural recovery process and timeframes, activity modification and exercise advice, information about use of pharmacological and non-pharmacological pain management, and what to do if they experience problems (such as flare ups of pain).

After the best practice therapy session, community physiotherapists local to the patients' home will be given access to study-trained physiotherapists at the recruiting hospital/regional specialist centre, to build a network of physiotherapy expertise in this rare disease.

Supporting materials for self-management will be provided on an online-platform and will include explainer videos and written information to guide recovery as acute pain settles and activity levels build up again. This will also be signposted on the web-platform to other places for further support from trustworthy sources, such as the STEPS charity website, which the CI and co-applicant already contribute to.

13.2.1 History of the development of the Non-STOP Therapy Package

The Non-STOP Therapy Package forms the Active Containment Intervention. Non-STOP, or the Non-Surgical Treatment of Perthes' Disease, was developed through an NIHR Fellowship by [name] (co-applicant). This was developed through a Delphi consensus process on the non-surgical management of Perthes' disease and a qualitative study [30], involving both key clinical stakeholders and children with Perthes' disease to define best practice. The development also included a systematic review of the non-surgical management of Perthes' disease and a case review of these interventions at five NHS centres [31, 32].

Interviews with children with Perthes' disease and their families emphasised the need to offer high-quality advice to support families not having surgical treatment. Parents told us they want reliable information and to be offered a credible alternative to surgery, i.e. feeling like 'something' rather than 'nothing' is being offered by the specialist centre. Traditional 'watch and wait' strategies from the specialist centre are consistently not considered acceptable by the parents and children that were consulted.

13.2.2 Training and fidelity of the Non-STOP Therapy Package

The OP Non-STOP study best practice therapy intervention will be manualised and physiotherapists delivering the intervention will be trained by the study team online and/or face-to-face.

Based on our experiences of delivering previous physiotherapy interventions, we are confident that a half to one day of training is sufficient. There will be fidelity assessments through the completion of

treatment logs by physiotherapists and observation of treatment sessions at sites by the central study research physiotherapist either in person or via audio-recordings.

13.3 Concomitant care

The interventions describe the two broad approaches to treatment which represent standard practice. No additional care, beyond standard care, is planned.

Community health professionals seeing trial participants will be made aware of the trial-trained physiotherapists with an interest in the treatment of Perthes' disease at recruiting centres to foster the development of best practice.

Families will be provided with online material to continue to facilitate their therapy at home. There will be ongoing support through the online platform and the network of therapists.

13.4 Measures to reduce the potential for cross-overs

The OP Non-STOP study team strengthened their understanding of this issue through qualitative interviews with patients, parents and clinicians [33, 34]. It is anticipated that there will be similar numbers of cross-overs in both directions.

Despite an in-depth consent discussion, after randomisation to the surgery group, some parents, in consultation with their treating clinicians, will choose not to have surgery. Likewise, other families allocated to active containment, in consultation with their treating clinicians, will choose to undergo surgery. The most appropriate course of treatment will be available for participants at all times, e.g. participants can transition between groups, or, if requested, be withdrawn from the study. We will monitor cross-overs closely (on a site-by-site basis) to identifytrends that emerge, and disseminate learning points gleaned throughout the study.

To minimise cross-overs, the OP Non-STOP study team will provide a package of information to sites, built on our learning and previous work with the QuinteT group [35], to ensure that the language clinicians use is optimised.

14 INFORMED CONSENT

14.1 Consent Procedure

If the family is interested in potentially participating in the OP Non-STOP study, they will be introduced to a member of the local study research team, and presented with the age-appropriate information materials, 'explainer video', a public website containing all relevant information and a verbal explanation of the study procedures. The family will then be given the opportunity to discuss issues related to the study with the clinical team, member of the research team, and family and friends ensuring that the potential participant and their family has sufficient time to consider participating or not. The parent will then be asked to sign an informed consent form (ICF) (only one parent will have to complete consent) and, where appropriate, children will be asked for their assent.

14.2 Time allowed to decide to take part

Participants and their families will be given as much time as they need to decide on whether to take part.

14.3 Completion of the Informed Consent Form

The potential participant, parent and the Investigator (or authorised designee) must personally sign and date the current approved version of the informed consent and assent forms as stated above.

The ICF and Assent Form will be offered to parents and potential participants in clinic/hospital as an electronic form on a tablet device (with the consent/assent forms completed directly on the study database, REDCap). Where it is not possible for a consent/assent forms to be completed in clinic (for example, if a participant has only had telephone appointments), remote electronic consent/assent may also be used.

With consent/assent forms completed electronically, signatures will be either achieved by a finger tracing across a tablet device, using an electronic stylus on a tablet device, or using a mouse dragging the cursor across the screen — all methods are to be used as if signing with a traditional pen. If the parent has an email address they are willing to provide, an electronic version of the signed ICF and assent form will be automatically emailed to them. If the parent does not have/does not provide an email address the site research team will be able to print a copy of the signed ICF and assent form and provide this to the parent. A copy of the electronic consent and assent form downloaded from the study database must be placed in the eISF and a copy in the participant's medical record.

14.4 Optional aspects of consent

Participants will be required to give their consent for all aspects of study participation to take part in the study. Consent for inclusion into the NAHR for long-term follow-up however, is optional.

14.5 Individuals lacking capacity to consent

There are circumstances where the recruiting team assess that the child does not have capacity to assent, or where the situation (i.e. pain and anxiety related to the condition and surgery) means that the child expresses a wish for the decision to be made solely by their parent. Therefore, the absence of assent does not exclude the child from the study if consent has been obtained from the parent/legal representative. If a child completes the assent form indicating that they do not wish to participate, they will not be included in the study.

14.6 Participants who lose capacity during the study

In the unlikely event that the participant loses capacity to consent during the study, the parent will decide whether it is in the best interest of the child to continue taking part in the study. In the unlikely event of the parent losing capacity, other parents/guardians can complete the questionnaires, or the participant would be withdrawn from the study. If withdrawn, de-identified data already collected with consent would be retained and used in the study. No further data would be collected, or any other research procedures carried out on or in relation to the participant.

14.7 Re-consenting

Should there be any subsequent amendment to the approved protocol, which might affect a participant's participation in the study, continuing consent/assent will be obtained using an amended consent /assent form which will be signed by the parent/participant.

15 RANDOMISATION

15.1 Timing of randomisation

Randomisation will only be performed when informed consent (and assent if applicable) has been obtained and eligibility confirmed.

15.2 Randomisation procedure

Eligibility will be reconfirmed at randomisation. Participants will be randomised by the site research team via a centralised validated computer randomisation program through a secure (encrypted) webbased service, incorporated and accessed via the OP Non-STOP study REDCap database enabled by OCTRU.

The patient will be randomised at an orthopaedic clinic/hospital visit. All hospital treatment areas have access to the internet so will access the randomisation service in real time. Participants will be randomised to one of the following arms:

Table 8: Intervention and comparator

| Arm | Treatment |
|------------------------------------|--|
| Containment surgery (intervention) | Children randomised to containment surgery will receive an operation on their hip. |
| Active containment (comparator) | Children and families will receive an individual face-to-face best practice therapy session of up to 90 minutes with a trial-trained physiotherapist at the recruiting hospital/ regional specialist centre. |

Upon randomisation of a participant, the OP Non-STOP study central team and a member of the site research team will be notified by an automated email.

Full details of the randomisation procedure will be stored in the Randomisation and Blinding Plan in the confidential statistical section of the eTMF.

15.4 Justification for stratification factors

Stratification by age group will ensure that the treatments are balanced across age groups which may be important since older children have a worse prognosis.

Stratification by sex will ensure that the treatments are balanced across the sexes which may be important since girls have a worse prognosis.

Stratification by collapse (lateral pillar height) will ensure that the treatments are balanced across femoral head severity as more collapse has a worse prognosis.

15.5 Back-up randomisation/registration procedure

There is no back-up randomisation procedure for this study as randomisation is not time critical.

16 SUB-STUDIES/TRANSLATIONAL STUDIES/MECHANISTIC STUDIES

There are currently no planned sub-studies/translational studies/mechanistic studies.

17 STUDY ASSESSMENTS/PROCEDURES AND DATA COLLECTION

The study flow chart can be found in Appendix 1 of this protocol.

17.1 Overview

Table 9 shows scheduled assessments for the study.

Table 9: Schedule of activities

| Assessments | Baseline | Intervention | 3 months post randomisation | 6 months post randomisation | 9 months post randomisation | 12 months post randomisation | 18 months post randomisation | 24 months post randomisation | 30 months post randomisation | 36 months post randomisation |
|---|----------|--------------|-----------------------------|-----------------------------|-----------------------------|------------------------------|------------------------------|------------------------------------|------------------------------|------------------------------|
| Demographics | * | | | | | | | | | |
| Status of Perthes' disease | * | | | | | | | | | |
| Randomisation | * | | | | | | | | | |
| Surgery / Best Practice Therapy Session | | * | | | | | | | | |
| PROMIS - Mobility | * | | * | * | * | * | * | * | * | * |
| Wong-Baker Faces Pain Scale | * | | * | * | * | * | * | * | * | * |
| CHU-9D | * | | * | * | * | * | * | * | * | * |
| PROMIS - Family Relationships | * | | * | * | * | * | * | * | * | * |
| Educational participation | | | * | * | * | * | * | * | * | * |
| Resource use Questionnaire | | | * | * | * | * | * | * | * | * |
| Complications (Additional care- participant reported) | | | | * | | * | * | | | * |
| Complications (site reported) | | | | | | | * | | | * |
| Collection of routinely available radiographs documenting the hip and pelvis appearance up to 36 months | | | | | | | | | | * |

17.2 Study questionnaires

Where possible, questionnaires will be completed electronically by the family. Families will be texted/emailed a link to complete their study questionnaires electronically. Any links to questionnaires sent to a family either by email or text is unique to a participant and their timepoint/questionnaire in the study. Telephone administered questionnaires may also be used where the use of electronic means is not possible for the family.

17.3 Data Collection

All follow-ups are collected electronically directly from the family, unless otherwise indicated.

The study will be made efficient and more environmentally friendly by ensuring that all outcomes are collected via SMS text message containing a link to an eCRF amongst those with a smart phone, an email link to an eCRF for those with internet access but no smart phone, or telephone for those with no smart-phone or web-access. We have employed this technique successfully across our broad portfolio of paediatric orthopaedic trials (FORCE, SCIENCE, CRAFFT) — which included 94% primary outcome completion in the FORCE study. Trial materials will be optimised using age-appropriate multimedia resources, developed with knowledge acquired through our prior work as part of the TRECA study (NIHR HS&DR) [26]. We will ensure that all trial materials are electronic to maximize efficiency.

17.3.1 Baseline assessment

Completed at hospital by local research team member with participant/and or their parent. For a full list of data collection, please see Appendix 2.

17.3.2 Intervention

Completed at hospital by local research team member. For a full list of data collection, please see Appendix 2.

17.3.3 Follow-up assessments/subsequent visits

For a full list of data collection please see Appendix 2.

17.4 Communication with study participants by the central study team

Participants will be notified to complete study questionnaires by email or text. Participants may be sent up to two reminder messages and/or where possible may be asked to complete questionnaires during a routine clinic visit. Participants that do not complete their study questionnaires may be telephoned to collect the data or request return of the electronic questionnaire. Participants will receive an initial email/text and up to two reminder messages from a member of the central study team to collect outcome data. A welcome letter will be sent out to participants upon recruitment into the study, as well as a reminder postcard at 12, 24, and 36 months.

17.5 Qualitative assessments

No qualitative research will be performed as part of the study.

17.6 Withdrawal

Withdrawal of consent means that a participant (and/or their parent) has expressed a wish to withdraw from the study altogether or from certain aspects of the study only. The type of withdrawal will be collected on the CRF labelled 'Withdrawal'.

The Withdrawal CRF should be completed to document the reasons for withdrawal and state who the decision to withdraw was made by. Discussions and decisions regarding withdrawal should be documented in the participant's medical notes. Investigators should continue to follow up any SAEs and should continue to report any SAEs to resolution in the CRF in accordance with the safety reporting section.

Where a participant/parent expresses a wish to withdraw from the study, the research team will determine which aspect(s) of the study the participant wishes to withdraw from.

The aspects of the study that the participant may request to withdraw from are as follows:

- No longer willing to complete study questionnaires but still willing to have routine data from the medical record provided to the study
- No longer willing to complete study questionnaires AND no longer willing to have routine data from the medical record provided to the study.

Where a participant/parent wishes to withdraw from all aspects of study participation, as detailed above this will be recorded on the Withdrawal CRF as full withdrawal.

In addition to participant self-withdrawal, an investigator may decide to withdraw a participant from the study intervention for clinical reasons or other reasons such as non-compliance or eligibility. Participants and their parent/guardian will still be asked to participate in the collection of follow-up data. The reason for withdrawal will be recorded on the study withdrawal CRF.

Completion of the Withdrawal CRF by the site research team will trigger a notification to the central study team. Appropriate action will be taken by the study teams (centrally and by the site research team at each participating site) to ensure compliance with the participant's withdrawal request. This may include marking future CRFs as not applicable and ensuring any communications regarding their participation are no longer sent.

Data collected up to the point of withdrawal will be used/analysed as explained in the PIS.

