23.2 Sample Size/Power calculations

172 participants providing data on the PROMIS Mobility Score for children at three years post randomisation (86 in each group) will provide 90% power to detect a difference in means of 5, assuming the standard deviation (SD) is 10 using a two group t-test with a 5% (2-sided) significance level. This is inflated to 216 participants (108 per arm) to allow for 20% attrition.

Raw scores of the PROMIS are translated into standardised T-scores with a population mean of 50 and an SD of 10.

The minimum clinically important difference (MCID) of PROMIS paediatric measures is generally 3.0-5.0 [29,30].

We discussed with children and families the size of the difference they would require to justify surgery, over optimised non-surgical containment. Given that surgery is a considerable intervention in the lives of the child and their family (i.e., the anaesthetic, the pain and scar, admission to hospital, the frequency of the requirement for a second procedure to removal metalwork, along with the lengthy

duration of immobilisation and recovery), families believed that the effect sought should be at the upper range of the MCID. Other studies have similarly highlighted that patients often seek greater effect sizes to warrant bigger surgical interventions than the established MCID [31].

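### Both withdrawal options in section 17.6 end all questionnaires, so a family that formally withdraws because of the interim forms has no recordable way to keep the 36-month primary outcome

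*Protocol*

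**What the plan says.** Protocol section 17.6 defines withdrawal as covering a participant or parent who "has expressed a wish to withdraw from the study altogether or from certain aspects of the study only". It then gives a list of two choices, presented as complete. The first is "No longer willing to complete study questionnaires but still willing to have routine data from the medical record provided to the study". The second ends the questionnaires in the same way and also ends the supply of medical-record data.

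Once the Withdrawal CRF is completed, the central team is notified and acts to comply with the family's request. Of that action the section says "This may include marking future CRFs as not applicable and ensuring any communications regarding their participation are no longer sent".

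For a child whom the investigator withdraws from the study intervention, the section adds "Participants and their parent/guardian will still be asked to participate in the collection of follow-up data". It has no corresponding sentence for withdrawal at the family's own request.

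The primary outcome is PROMIS Mobility at 36 months (sections 9.2 and 23.3.1). It is reported by a parent for every child (section 9.3) and collected as a computer adaptive test, by telephone if the family prefers (section 10.9). On sample size, section 23.2 says of the 172 evaluable children needed: "This is inflated to 216 participants (108 per arm) to allow for 20% attrition".

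**The concern.** The two options differ only in whether medical-record data continue. Neither separates the seven interim rounds from the one round that carries the primary outcome. A family that asks to withdraw at, say, 9 or 12 months because the forms are a burden must be recorded under a category that also gives up the 36-month score. The routine data kept under the first option do not replace it, because the score exists only as a parent's questionnaire answers.

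What is at stake is avoidable missing data on the primary endpoint. The primary model (section 23.3.1) uses the baseline score, the 36-month score, treatment and the minimisation factors. It uses no interim score, so one contact at 36 months would make such a child fully evaluable. The principal analysis takes participants with available outcome data (section 23.4), and families know their allocation (section 18.1). Missing scores therefore cost some precision and leave room for bias that the analysis can examine but not remove.

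**Working it through.** **1. Which options keep the primary outcome**

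| Situation | Interim questionnaires | 36-month PROMIS Mobility | Routine data |
|---|---|---|---|
| Family withdraws, first option (17.6) | stop | stop | continue |
| Family withdraws, second option (17.6) | stop | stop | stop |
| Investigator withdraws child from the intervention (17.6) | still requested | still requested | not separately stated |
| Family leaves forms unanswered without withdrawing (17.4) | reminders, clinic completion or telephone | still requested | continue |
| Family withdraws from interim forms only | no category | no category | no category |

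The gap is the last row.

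**2. Questionnaire load (Table 9, section 17.1)**

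There are eight rounds after baseline: 3, 6, 9, 12, 18, 24, 30 and 36 months. Seven are interim. Six instruments are asked at every round: PROMIS Mobility, Wong-Baker, CHU-9D, Family Relationships, educational participation and resource use. The participant-reported complications form is asked at 6, 12, 18 and 36 months.

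6 × 8 + 4 = 52 instrument completions per family after baseline, of which one is the primary outcome. This counts instruments, not time; some of them are very short.

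**3. The plan's own sample size (section 23.2)**

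Inputs: difference 5, SD 10, two-sided 5% level, 90% power, two-sample t-test, 1:1 allocation.

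- The exact t-test solution is 85.03 per arm, rounded up to 86 per arm or 172 in total. Power at 86 per arm is 90.3%.
- Inflation: 86 / (1 − 0.20) = 107.5, rounded up to 108 per arm or 216 in total.

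The stated figures reproduce. After 20% loss, 216 × 0.80 = 172.8 remain against 172 needed, so there is almost no slack. Total loss of 25% (162 left) would give 88.5% power, and 30% (151.2 left) would give 86.3%.

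**4. Illustration of what a further option could recover**

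The protocol gives no rate for formal withdrawal and none for willingness to answer once at 36 months. Both shares below are assumptions.

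- Allowed loss: 0.20 × 216 = 43.2, about 43 children.
- Assume half are formal questionnaire withdrawals: 43.2 / 2 = 21.6, about 22.
- Assume 30% to 50% of these would accept one contact at 36 months: 0.30 × 21.6 = 6.5 and 0.50 × 21.6 = 10.8, so about 6 to 11.
- Evaluable children: 172 + 6 = 178 to 172 + 11 = 183.
- Power by the same t-test: 90.3% at 172, 91.3% at 178, 92.0% at 183.

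**The case against.** The strongest reply is that not filling in interim forms is not withdrawal under this protocol. Section 17.4 handles non-completion separately, with up to two reminders, completion at a routine clinic visit, a telephone call, and a postcard at 36 months. Section 25.7 promises monitoring of responses at all time points, and section 31 offers a voucher after each annual follow-up. Nothing says that missed rounds end follow-up. This stands. A reader might infer that any family tired of the interim forms is lost to the primary outcome, and the protocol does not support that. The gap concerns only families recorded on the Withdrawal CRF.

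Second, a reader might infer that the form automatically closes future CRFs and contact. Section 17.6 says only that the action may include these steps and that it follows the family's request. The team must also first establish which aspects the family wants to leave. That discretion is real, but the list gives no category in which to record a wish to stop the interim forms alone.

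Third, the first option already is a partial withdrawal, so section 17.6 does not contradict itself. That is fair. The weakness lies in what the list omits.

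Fourth, a reader might infer that these losses follow recovery, dissatisfaction or treatment arm. The protocol offers no evidence for this. Changing treatment does not remove a child from follow-up (sections 13.4 and 23.4), and section 23.8 plans multiple-imputation sensitivity analyses, including departures from missing at random, if missingness is sufficient or differential. Outcome-related loss is possible in an unblinded trial but is not shown. Imputation, for its part, does not recover a score that was never requested.

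Finally, the Withdrawal CRF itself is not available and might offer finer choices. The list in section 17.6 nevertheless reads as complete, and the form would be expected to follow it.

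**Conclusion.** The point holds in a limited form. As written, section 17.6 gives a formally withdrawing family no recordable way to stop the interim questionnaires and keep the 36-month PROMIS Mobility score, and no other source in the trial can supply that score.

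The number of families affected cannot be taken from the protocol. Under the two assumed shares, 6 to 11 outcomes would be recovered and power would rise by about 1 to 2 percentage points. The 20% allowance also covers silent non-response, which this change does not address, and the sample size calculation is correct. The case therefore rests less on power than on preventing avoidable missing primary data, given that the principal analysis uses available data only and the attrition allowance has almost no slack. It is a cheap improvement to make, not a flaw that threatens the trial. An analysis plan cannot make it, because the withdrawal categories belong to the protocol, the CRF and the information sheet.

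**What to change.** Add one option to section 17.6 and to the Withdrawal CRF. Offer it only when a family asks to withdraw, and before the two existing options. Suggested wording: *No further interim questionnaires, but willing to be asked for PROMIS Mobility once at 36 months (link or telephone) and for routine data to be used.* Both existing options remain.

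For families who choose it, suppress only the 3- to 30-month questionnaire contacts and keep the 36-month contact active. State in section 17.6 that future CRFs other than the 36-month PROMIS Mobility are the ones to be marked not applicable.

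The cost is one CRF field, a change to the database contact logic, and matching information-sheet wording, with whatever amendment approval that requires. These families would give no interim secondary, CHU-9D or resource-use data, but the present options lose those data anyway. A few families might choose the new option instead of continuing in full; offering it only on a request to withdraw limits that.
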